6.7.6.5. Adverse Event Recording and Reporting

The Investigator must record all AEs that occur from the time written informed consent is obtained until 30 days after the patient's last dose of the last course of RC-P, regardless of their relationship to study drug.

In addition, any SAE assessed as related to study drug by the Investigator that occurs more than 30 days after the patient's last dose of the last course of RC-P, must be reported as described below.

Serious AEs must be reported to the Sponsor or its designee using an SAE Reporting Form within 24 hours of first knowledge of the event by study site personnel. The reporting form and contact information for submission of the form, will be provided to the study sites separately.

The reporting form must be completed as thoroughly as possible before transmittal to the contact provided on the form. The Investigator must provide his/her assessment of causality to the study drug and study procedure at the time of an initial SAE report. If the Investigator's assessment of causality changes after the initial report, it must be provided as follow-up information to the Sponsor.

Other Reportable Experiences:

Overdose, (defined as any dose administered or received that was higher than the intended dose), medication errors (defined as any unintentional error in the dispensing or administration of the study drug), and misuse of the study drug are considered reportable experiences and should be reported by study site personnel on an Other Reportable Experience Form. The form, and contact information for submission of the form, will be provided to the study sites separately.

If any overdose, medication error or misuse of the study drug results in an AE this must be recorded, and if this AE is serious it must also be reported as described above.

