## 5. STUDY DESIGN

### 5.1. Summary of Study Design

This study is designed to assess the tolerability and efficacy of RC-P (only in patients with ALL/LBL who develop hypersensitivity to an *E. coli*-derived asparaginase), as measured by asparaginase activity. In this patient population, 6 doses of RC-P should be substituted for each dose of a long-acting *E. coli*-derived asparaginase. Two consecutive weeks' treatment of RC-P is defined as one course. Additional courses of RC-P will be administered based on each patient's original treatment plan for as long as the patient derives clinical benefit.

This study will consist of two parts: **Part A** to determine the dose of RC-P for IM administration and to confirm safety and efficacy; and **Part B** to define the optimal dose and schedule of IV RC-P. Part A and Part B may be investigated in parallel.

Efficacy and safety data will be assessed by a Study Data Review Committee (SDRC) at frequent intervals as described below. The SDRC will make recommendations and have oversight of the study as described in the protocol and the SDRC Charter. The SDRC will review results throughout the study as follows: for Part A at n = 6 and 13 (for each Cohort 1 subcohort), at n = 19, 32, and 51 (Cohort 1 plus Cohort 2 at the final IM RC-P dose with n=51 as the interim analysis); and Part B at n = 6 at a minimum.

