### 10.2. Adverse Events

AEs recorded in the case report form will be coded to system organ class (SOC) and preferred term (PT) using the Medical Dictionary for Regulatory Activities (MedDRA 22.1). The investigator will assess the relatedness of each AE to study drug. The severity of AEs will be recorded using the Common Terminology Criteria for Adverse Events (CTCAE 5.0).

At a minimum, the investigator must record all AEs that occur from the time written informed consent is obtained until screen failure if applicable, or 30 days after the patient's last dose of the last course of RC-P, regardless of their relationship to study drug. Any serious AE (SAE) assessed as related to study drug by the investigator that occurs more than 30 days after the patient's last dose of the last course of RC-P should be reported regardless of time after study termination.

A treatment-emergent adverse event (TEAE) is defined as any event with onset date on or after Study Day 1 through the end of the study or any ongoing event that worsens in severity after Study Day 1 through the end of the study. Only TEAEs with the onset date through the end of the AE reporting period will be included in summary tables unless otherwise specified. For the purpose of calculating treatment emergence, incomplete onset dates will be imputed as detailed in [Appendix I](#).

AEs are graded by the investigator as Grade 1 (mild), Grade 2 (moderate), Grade 3 (severe or medically significant but not immediately life-threatening), Grade 4 (life-threatening consequences), or Grade 5 (Death related to AE). The severity grade of events for which the investigator did not record severity will be categorized as "missing" for tabular summaries and data listings, and will be considered the least severe for the purposes of sorting for data presentation.

Treatment-related AEs are those for which the investigator answers "Yes" to the question "Was this adverse event related to study treatment?" in the eCRF. Events for which the investigator did not record relationship to study treatment will be considered related to study treatment for summary purpose. Data listings will show treatment-relationship as missing. AEs for which "Yes"

Jazz Pharmaceuticals Ireland Limited  
Statistical Analysis Plan – Protocol JZP458-201

is marked for question “Was this adverse event related to study procedure?” in eCRF will be identified and included in AE listing.

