SAEs are those for which the investigator answers “Yes” to the question “Was the adverse event serious?” in the eCRF. The clinical database will be reconciled with the SAE database before database finalization.

For all AE summaries, if a patient has more than 1 AE within a PT, the patient is counted only once at the maximum severity and with the closest relationship to study drug. If a patient has more than 1 AE within a SOC, the patient is similarly counted once when reporting results for that SOC.

A brief summary of TEAEs (i.e., the number and percentage of patients) will be presented by dose level of RC-P, and route of administration (IM or IV) for the following: (1) any TEAE, (2) any serious TEAE, (3) any treatment-related TEAE, (4) any serious treatment-related TEAE, (5) any Grade 3 or 4 TEAE, (6) any treatment-related Grade 3 or 4 TEAE, (7) any TEAE leading to study drug discontinuation, (8) any treatment-related TEAE leading to study drug discontinuation, (9) any TEAE leading to death, and (10) any treatment-related TEAE leading to death.

A general summary of TEAEs by SOC and PT will be provided with the number and percent of patients who experienced the following types of events by dose level of RC-P, and route of administration (IM or IV). For data presentation, SOC will be ordered alphabetically, with PT sorted by decreasing frequency in the final dose of IM:

- Patients with any TEAE
- Patients with any serious TEAE
- Patients with any treatment-related TEAE
- Patients with any serious treatment-related TEAE
- Patients with any Grade 3 or 4 TEAE
- Patients with any treatment-related Grade 3 or 4 TEAE
- Patients with any TEAE leading to study drug discontinuation
- Patients with any treatment-related TEAE leading to study drug discontinuation
- Patients with any TEAE leading to death
- Patients with any treatment-related TEAE leading to death

Data listings will be provided for the following including patient number, dose level of RC-P, route of administration (IM or IV), SOC, PT, date of onset/stop, severity, seriousness, treatment-relationship, action taken:

- All AEs
- Serious AEs
- Treatment-related AEs
- Serious treatment-related AEs
- Grade 3 and 4 AEs

Jazz Pharmaceuticals Ireland Limited  
Statistical Analysis Plan – Protocol JZP458-201

- AEs leading to study drug discontinuation
- Death report

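### An AE starting more than 30 days after a course is tabulated if another course follows and left out if none does, so the death and discontinuation tables can miss events in that interval

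*SAP*

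**What the plan says.** - **TEAE definition.** SAP 10.2 counts as treatment-emergent "any event with onset date on or after Study Day 1 through the end of the study", together with ongoing events that worsen over that time.
- **Table rule.** The next sentence is narrower: "Only TEAEs with the onset date through the end of the AE reporting period will be included in summary tables unless otherwise specified".
- **The period.** The SAP does not define the AE reporting period separately. The preceding paragraph of SAP 10.2 sets, as a minimum, a recording period with the same end as Protocol 6.7.6.5: "The Investigator must record all AEs that occur from the time written informed consent is obtained until 30 days after". In both documents those 30 days are counted from the final dose of whichever course proves to be the last. For serious events judged related that occur later, SAP 10.2 says they "should be reported regardless of time after study termination", but no sentence places them in the tables.
- **Courses.** Under SAP 5.1, further courses follow each patient's "original treatment plan for as long as the patient derives clinical benefit". Neither document gives the interval between courses.
- **Tables.** SAP 10.2 asks for rows such as "Patients with any TEAE leading to study drug discontinuation", and for TEAEs leading to death, without giving either a different window.

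**The concern.** Which course is the last is settled only by what happens afterwards. Take two patients who have finished Course 1, have Course 2 planned, and have the same event 45 days after their last dose. In the first, Course 2 goes ahead, the last dose moves forward, and day 45 lies inside the reporting period. In the second, Course 2 is never given, the period closed on day 30, and the event lies outside it. The event itself can decide which patient is which.

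Two tables are affected by construction. A fatal event always prevents the next course, and so does an event that permanently stops RC-P. If either starts on day 31 or later between courses, it cannot appear in the table meant to show it.

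The occurrence of TEAEs determines the primary safety endpoint (SAP 4.2.1). With about 98 patients at the final IM dose, a few events would visibly change a death or discontinuation row.

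**Working it through.** **1. The plan's own figure.** Protocol 3.4 gives about 72 days in the study for a one-course patient. Screening 28 + course 14 + follow-up 30 = 72, which reproduces it. The 30 days run from the last dose of the last course.

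**2. Which end date does the table rule mean?** If the AE reporting period simply ran to the end of the study, the restriction would add nothing to the TEAE definition just before it. The 30-day end is the only other one described, so it is the natural reading. It remains an inference, because the term is undefined.

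**3. Classify an onset on day d after the last dose of a course**, where G is the number of days to the next planned course and d ≤ G.

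| Onset | Later course given | No later course |
|---|---|---|
| d ≤ 30 | tabulated | tabulated |
| 30 < d ≤ G | tabulated | left out |

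**4. Share of the gap affected.** G is not in the documents, so the values below are assumptions, with onset spread evenly over the gap. The share left out when RC-P ends is max(0, G − 30)/G. When RC-P continues, it is 0 for every G.

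| Assumed G (days) | Onset days tabulated if RC-P continues | Onset days tabulated if RC-P ends | Share left out if RC-P ends |
|---|---|---|---|
| 14 | 14 | 14 | 0% |
| 21 | 21 | 21 | 0% |
| 30 | 30 | 30 | 0% |
| 42 | 42 | 30 | 12/42 = 28.6% |
| 56 | 56 | 30 | 26/56 = 46.4% |
| 70 | 70 | 30 | 40/70 = 57.1% |
| 84 | 84 | 30 | 54/84 = 64.3% |

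**5. Can this become a number of patients?** That needs q, the proportion of patients with a treatment-ending event in a gap, which the documents do not give either. The formula is 98 × q × (G − 30)/G.
- q = 1%, G = 45: 98 × 0.01 × 15/45 = 0.3 patients.
- q = 10%, G = 90: 98 × 0.10 × 60/90 = 6.5 patients.

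A range from 0.3 to 6.5, and zero if no gap exceeds 30 days, shows only that the documents do not fix the size.

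**6. Agreement between outputs.** SAP 8.2 summarises reasons for discontinuing study drug with no onset window, and the listings in SAP 10.2 state no cut-off. A patient who stops for an event on day 45 would be in both, yet absent from the TEAE discontinuation table.

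**7. Agreement over time.** SAP 3 plans interim, primary and final analyses, and SAP 8.2 has a category for patients still on treatment. A patient between courses at the primary analysis has no settled last course. An event on day 45 could be tabulated then and drop out at the final analysis if RC-P never resumes. The SAP has no rule for this.

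**The case against.** The case on the other side is that the SAP has only left a term undefined. The 30-day limit is written as a minimum for recording, related serious events are reported whenever they occur, and disposition and the listings would show the patients concerned. The primary efficacy endpoint is untouched, and no formal safety testing is planned.

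Much of this stands, and it rules out several stronger readings.
- *Every between-course event that ends RC-P is lost.* No: onsets on days 1 to 30 count either way, and gaps of 30 days or less are unaffected.
- *Only treatment-ending events are removed.* No: the window closes whenever no later course is given, including after withdrawal of consent, pregnancy or a sponsor decision (Protocol 6.8.1). Events that did not cause the stop are left out too.
- *The events disappear from the report.* No: they leave the summary tables, not disposition or the listings.
- *The serious, related and special-interest tables are shown to be biased.* They are affected only where such an event falls after day 30 with no later course. SAP 10.2.1 also speaks of AEs rather than TEAEs, so it is unclear that the restriction reaches that summary.
- *A safety stopping decision would change.* Nothing in the documents shows this. The committee reviews of Cohort 2 are triggered by completion of Course 1.

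What does not stand is that this is merely a missing definition. Followed on its natural reading, the rule makes inclusion depend on outcome, and listings do not replace the tables that present the primary safety endpoint.

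**Conclusion.** The concern holds for onsets more than 30 days after the last dose given, while another course is still planned. Those events are tabulated if a later course is given and left out if none is. Fatal and treatment-ending events in that interval therefore miss the two tables designed for them, which makes those tables look more favourable.

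This rests on reading the AE reporting period as the 30-day recording period. The size is unknown and may be zero. The percentages above depend on assumed gaps and even onset, and no patient count can be supported. No sample size or power figure changes. The change is worth making because it concerns a primary endpoint and costs little.

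**What to change.** In SAP 10.2:

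1. Define the end of the AE reporting period, and state how a patient who is between courses at an interim or primary analysis is handled.
2. Always include any TEAE recorded as fatal, or as the reason RC-P was stopped, in the death and discontinuation tables and in the matching serious, Grade 3/4, related and special-interest rows, whatever its onset relative to the last dose.
3. Add a supportive TEAE summary on the SAP's own definition, from Study Day 1 through the end of the study, so that inclusion of a recorded event does not depend on whether another course followed. Say that this means the end of the overall study. The protocol also uses the end-of-study label for the visit 30 days after the last dose, and that meaning would bring the same dependence back.

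Merely extending the window to the date RC-P was permanently discontinued would not be enough. With a decision to stop on day 40, an unrelated event on day 45 would still be excluded, yet the same event would count if Course 2 were given.

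The cost is SAP wording, a derived date and one extra summary. Discontinuation reasons are already captured, and events arising while a further course is planned are already recorded. The downside is that a few later-onset events enter the tables, so rates may look slightly less favourable.

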8.9. Safety Analysis

The safety and tolerability evaluations of IM RC-P in patients with ALL/LBL who are hypersensitive to *E. coli*-derived asparaginases will be assessed by the occurrence of treatment-emergent adverse events (TEAEs) for the Safety Analysis Set.

The incidence of TEAEs for the Safety Analysis Set will be summarized by dose level in Part A and Part B. Adverse events will be coded using the Medical Dictionary for Regulatory Activities (MedDRA) to classify events under primary system organ class and preferred term. In addition, TEAEs, serious TEAEs, TEAEs leading to discontinuation of study drug, CTCAE Grade 3 or above TEAEs, TEAEs related to study drug, and deaths (if any) will be summarized and/or listed as appropriate.

RC-P
Protocol Amendment 02: JZP458-201

Jazz Pharmaceuticals Ireland Limited

Descriptive statistics (n, mean, standard deviation, median, minimum, and maximum) as well as changes from Baseline (ie, the latest non-missing value obtained prior to or at the start date and/or time of the first dose of IM RC-P) will be presented by dose level in Part A and Part B for vital signs and clinical laboratory results.

No formal statistical testing will be performed for the safety analyses.

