### **7.5. Changes to Planned Analyses**

Sensitivity analyses were added to assess COVID-19 impact on the primary (Section 9.1.3) and key secondary (Section 9.2.3) efficacy endpoint. Additional subgroup analyses for the primary (Section 9.1.4) and secondary (Section 9.2.4) efficacy endpoints which are not specified in the protocol may be performed.

Summary of protocol deviations due to COVID-19 was newly added in Section 13.

Jazz Pharmaceuticals Ireland Limited  
Statistical Analysis Plan – Protocol JZP458-201

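### Do the SAP's Grade 3 or 4 adverse-event tables, and its Grade 2 versus Grade 3 split of prior reactions, leave out patients the protocol counts?

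*SAP*

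**What the plan says.** **Severity of adverse events.** Protocol 8.9 plans that "CTCAE Grade 3 or above TEAEs, TEAEs related to study drug, and deaths (if any) will be summarized and/or listed as appropriate". SAP 10.2 grades events on a five-point scale whose top level is worded "or Grade 5 (Death related to AE". Its brief overview has rows "5) any Grade 3 or 4 TEAE, (6) any treatment-related Grade 3 or 4 TEAE" and, separately, "9) any TEAE leading to death, and (10) any treatment-related TEAE leading to death". The tables by system organ class and preferred term repeat the same categories. The listings include one for "Grade 3 and 4 AEs", one for all adverse events and a death report, with fields that include "SOC, PT, date of onset/stop, severity, seriousness". For counting, a patient with several events in one preferred term is handled so that "the patient is counted only once at the maximum severity and with the closest relationship to study drug".

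**Record of changes.** SAP 7.5 begins "Sensitivity analyses were added to assess COVID-19 impact on the primary" and goes on to the added subgroup analyses, which it says may be performed. It does not mention the severity cut.

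**Grade of the prior allergic reaction.** Inclusion criterion 3 (Protocol 4.1) requires Grade 3 or higher for Cohort 1 and Grade 2 or higher for Cohort 2, or silent inactivation. Protocol 4.2 excludes no grade of prior allergic reaction. SAP 7.4 lists Grade 2 against Grade 3 as a subgroup split, and SAP 8.3 lists Grade 2, Grade 3 and silent inactivation as baseline categories. SAP 7.4 calls the subgroup analyses exploratory and optional, while SAP 9.1.4, 9.2.4 and 10.2.1 say they will be done.

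**The concern.** Read literally, the SAP is narrower than the protocol in one place and narrower than the eligibility criteria in another.

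First, a patient whose only severe event was fatal would be missing from the rows for severe events. Safety is a primary objective, and the protocol names deaths and Grade 3 or above events as two separate items, so a death row does not obviously stand in for the second. No planned row gives the combined count, and SAP 7.5 does not record the narrower cut.

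Second, a patient with a prior Grade 4 reaction has no named level in the baseline table or in the grade split used for the efficacy endpoints and the adverse events of special interest. The level in doubt is not a small one. If the 20% target for Grade 2 entrants to Cohort 2 holds, at most 0.20 × 85 = 17 patients enter on Grade 2, which leaves at least 98 − 17 = 81 with Grade 3 or higher or silent inactivation.

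At stake would be an understated severe-event rate and a subgroup table that drops eligible patients.

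**Working it through.** The plan states no figure for this point, so there is none to reproduce. The check sets the passages side by side and then bounds the effect.

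**1. Is each grade in Protocol 8.9 covered by SAP 10.2?**

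| Protocol item | Where the SAP reports it |
|---|---|
| Grade 3 and Grade 4 events | Overview rows 5 and 6; tables by organ class and preferred term; dedicated listing |
| Grade 5 events | Overview rows 9 and 10; tables by organ class and preferred term; death report |
| Any grade, patient by patient | Listing of all adverse events, with severity |

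All three grades are tabulated and listed. The protocol allows summary or listing as appropriate and does not require one combined row. The Grade 3 or 4 row is therefore correct under its label. Separate rows for fatal and non-fatal severe events are a choice of presentation, and SAP 7.5 has no dropped analysis to record.

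**2. How far can the Grade 3 or 4 row lie from a combined row?** Let *a* be the number of patients with a Grade 3 or 4 event, *d* the number with a fatal event, and *b* the number in both. The combined count is *a* + *d* − *b*. It lies between max(*a*, *d*) and *a* + *d*, and the listings give *b* exactly. The Grade 3 or 4 row is lower by *d* − *b* patients, or (*d* − *b*)/N.

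- Final intramuscular dose, N = 98 planned (SAP 5.3): 1/98 = 1.0 percentage point per such patient.
- Enrolment stopped at the interim, N = 51: 1/51 = 2.0 points.
- The documents give no rate of fatal events. For an assumed 0 to 3 such patients at N = 98, the gap is 0 to 3/98 = 3.1 points.
- For the small cohorts, 1/13 = 7.7 and 1/6 = 16.7 points are upper bounds once the targets are met. The 13 and 6 are targets for evaluable patients (Protocol 3.1.1 and 3.1.3.2). The adverse-event tables use the Safety Analysis Set, which is everyone given at least one dose and may be larger.

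The 1/98 and 1/51 figures are upper bounds for the same reason. In every case the patient appears in the death rows.

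**3. Does the counting rule hide anyone?** Protocol 6.7.6.2 records an increase in severity as a new event. Suppose an event rises from Grade 4 to Grade 5 within one preferred term. If the grade filter is applied first, the patient is in both the Grade 3 or 4 count and the death count. If maximum severity is taken first, the patient is in the death count only. Under either order the patient is reported.

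**4. Does any decision use these rows?** The toxicity limit for a Cohort 1 subcohort (Protocol 3.1.3.3) has its own definition, Grade 3 or higher, and is applied by the Study Data Review Committee. The limits for Cohort 2 concern allergic reactions, pancreatitis and thrombosis and use no Grade 3 or 4 cut. The primary endpoint is an enzyme-activity level. None of these reads from the severe-event rows.

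**5. Where would a prior Grade 4 patient go?** Criterion 3 divides patients at Grade 2 versus Grade 3 or higher, and the protocol synopsis describes the population as having moderate or severe reactions. The natural reading of the SAP's two levels is that same division, with Grade 4 pooled with Grade 3. The patient also stays in every overall analysis, in the age split, and in the split of allergic reaction against silent inactivation.

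**The case for a change.** The strongest case for a change is that it costs a few words and removes discretion from the programmer. The combined count cannot be had by adding two rows, because a patient may be in both. Someone who wants the figure named in the protocol must go to patient-level listings. The order of grade filter and maximum severity is not stated, and a Grade 3 or above cut would make that order irrelevant for the all-cause rows. For prior reactions, the SAP nowhere says that Grade 3 means Grade 3 or above, and three of its sections treat the subgroup analyses as firm.

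All of this is accurate, and it stands as a point of drafting. It does not show that the plan as written gives a wrong or misleading result. The Grade 3 or 4 row is low only against a combined row that the protocol does not ask for, and fatal events are displayed more prominently by having rows of their own. The reading needed for prior Grade 4 reactions is supplied by the protocol's own eligibility rule, in an analysis that SAP 7.4 and 7.5 both describe as optional.

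**Conclusion.** No change to the plan follows. The severity wording is a choice of presentation that leaves no fatal event unreported, and the prior-reaction wording is a shorthand that an analyst would fill in from inclusion criterion 3.

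At the planned 98 patients, the Grade 3 or 4 row can differ from a combined row by at most 1.0 percentage point for each patient whose only severe event was fatal. The difference is zero if there is no such patient. If no patient had a prior Grade 4 reaction, the subgroup and baseline counts are also unaffected.

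This rests on three assumptions: that the separate death rows and listings are produced as SAP 10.2 describes, that Grade 4 prior reactions are pooled with Grade 3, and that readers take the severe-event row under its stated label. Safety is reported descriptively, with no formal test, so no inference turns on the choice.
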